8.5 STUDY SIZE

The results from the feasibility evaluation showed that some large centres recruited more than 100 patients. To avoid large centres being overrepresented in the study population, it is planned to put a cap of 30 patients as the maximum number of patients that a single centre can recruit for either the medical record abstraction component or survey component of the study. To compensate for the 30-patient cap, the recommendation in the feasibility evaluation was to recruit 10-15 infusion centres per country in order to accomplish the recruitment targets for both components of the study.

Medical Record Abstraction Component Study Size

From the estimates obtained in the feasibility evaluation, the Sponsor projects that 20-30 patients per infusion centre will be recruited for the medical record abstraction component of the study, yielding a total of between 1,000 and 1,500 medical records collected during the 10-month period. Because the sample size for the medical record abstraction component of the study will be larger than that for the survey component, there will be greater precision around the estimates of MabThera use by whether the disease indication (RA, SLE/LN, other) represents on-label or off-label use. For example, with a sample of 1,500 patients, if 75% those abstracted are identified as on-label use, then the 2-sided 95% confidence interval (CI) will be 72.8% to 77.2%.

Survey Component Study Size

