Considering the estimates of the volume of patients available that were provided by the feasibility evaluation, during a 10-month period, a maximum of 720 patients could be recruited for the survey component in the 5 countries, assuming a mean (median) of 23-24 (13-18) patients per centre and 30 participating centres. However, the mean is based on some large centres recruiting more than 100 patients. To avoid large centres being overrepresented in the study population, it is planned to put a cap of 30 patients as the maximum number of patients that a single centre can recruit. The final study size has been set at 500 completed surveys across all countries, with an estimated 10-14 patients recruited per infusion centre for the survey; this will allow reasonable precision around estimates of patient knowledge and understanding of the PAC at the study level. Since it is planned to recruit up to 10-14 patients per infusion centre for the survey, the responses from patients within the infusion centre may be correlated. Assuming no correlation and the percentage of correct responses to a question (or the percentage with off-label use) is 75%, then for a sample of size 500, the 2-sided 95 CI will be 71.2% to 78.8%; whereas the corresponding CI will be 68.3% to 81.7% if there are on average 8 patients per infusion centre with an intra-class correlation of 0.3. A correct response rate of 50% yields the widest possible CI and thus the least precision; the farther the percentage is from 50%, the greater the precision. Table 1 shows 95% confidence limits assuming various combinations of sample size, percentage with correct response, and intra-class correlation coefficients.

Table 1 Confidence Limits for Various Combinations of Sample Size and Correct

Response Percentage

Patient Sample Size	Intra-class Correlation Coefficient ^a	Correct Response ^b (%)	Lower 95% Confidence Limit (%)	Upper 95% Confidence Limit (%)
100	0	25	16.5	33.5
100	0	50	40.2	59.8
100	0	75	66.5	83.5
100	0	90	84.1	95.9
100	0.15	25	12.8	37.2
100	0.15	50	36.0	64.0
100	0.15	75	62.8	87.2
100	0.15	90	81.6	98.4
100	0.3	25	10.1	39.9
100	0.3	50	32.7	67.3
100	0.3	75	60.1	89.9
100	0.3	90	79.6	100.0
500	0	25	21.2	28.8
500	0	50	45.6	54.4
500	0	75	71.2	78.8
500	0	90	87.4	92.6
500	0.15	25	19.6	30.4
500	0.15	50	43.7	56.3
500	0.15	75	69.6	80.4
500	0.15	90	86.2	93.8
500	0.3	25	18.3	31.7
500	0.3	50	42.3	57.7
500	0.3	75	68.3	81.7
500	0.3	90	85.4	94.6
1500	0	25	22.8	27.2
1500	0	50	47.5	52.5
1500	0	75	72.8	77.2

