1500	0	90	88.5	91.5
1500	0.15	25	21.9	28.1

Patient Sample Size	Intra-class Correlation Coefficient ^a	Correct Response ^b (%)	Lower 95% Confidence Limit (%)	Upper 95% Confidence Limit (%)
1500	0.15	50	46.4	53.6
1500	0.15	75	71.9	78.1
1500	0.15	90	87.8	92.2
1500	0.3	25	21.1	28.9
1500	0.3	50	45.5	54.5
1500	0.3	75	71.1	78.9
1500	0.3	90	87.3	92.7

Note: Table calculations assume an average of 8 patients from each practice (cluster).

Calculations performed using SISA software, prevalence module. Uitenbroek DG. Binomial. SISA. 1997. Available at: http://www.quantitativeskills.com/sisa/calculations/preval.htm. Accessed 11 June 2012.

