8.6 DATA ANALYSIS

Analysis of MabThera off-label use and evaluation of PAC knowledge and utilisation will be descriptive in nature and will entail the tabular display of summary statistics and the frequency distribution of item responses.

A detailed analysis plan describing methods of analysis and presentation, as well as table shells, will be developed prior to starting analysis of data. In addition to describing the analysis of off-label use, for the questionnaire data, the analysis plan will describe any planned comparisons of participants and non-participants. The analysis plan will also describe the following:

- Analysis of subgroups
- · Methods for handling missing data
- Level of statistical precision

All analyses will be performed using SAS 9.2 (or higher) statistical software (SAS Institute Inc., Cary, North Carolina, USA). Programs, logs, and output will be reviewed for accuracy according to relevant standard operating procedures.

The analysis of off-label use will be descriptive and will present MabThera utilisation by indication (RA, SLE/LN, other). Results will be evaluated by site characteristics, including country and geographic region within country, to ascertain any patterns of prescribing by specific indication. The main analysis will be to estimate (with 95% CIs)

^a With an average cluster size of 8 patients, correlation coefficients of 0.15 and 0.30 correspond with design effects of 2.05 and 3.1, respectively.

^b The percentage in this column does not need to represent only the percentage of correct responses; it can represent any percentage, for example percentage of abstractions that were identified as off-label use or percentage of abstractions that had systemic lupus erythematosus (SLE).

the proportion of off-label use among users of MabThera during the entire study period in the 5 European countries of interest. The proportion of each of the most common off-label use indications will be described among the entire off-label use group. In addition, an estimate of off-label usage will be determined amongst prevalent (i.e., repeat infusions) and incident (i.e., patients attending for their first MabThera infusion) patients to the extent that incident use can be accurately determined. Characteristics of patients meeting the definitions for both strict and broad on-label use will also be evaluated. The dosage of MabThera used by infusion will also be estimated in the on- and off-label groups.

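### Table 1's clustered n = 1,500 rows assume 8 patients per centre, but 20-30 records per centre are planned, so precision for the off-label estimate is overstated

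*Protocol*

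**What the plan says.** All of this is in Protocol Section 8.5 unless noted.

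- **Records.** The plan is 1,000-1,500 records: "the Sponsor projects that 20-30 patients per infusion centre will be recruited for the medical record abstraction component of the study". The text says this component will be more precise than the survey because its sample is larger. Its example, 72.8-77.2% for 75% on-label use with n = 1,500, has no allowance for clustering.
- **Survey.** "The final study size has been set at 500 completed surveys across all countries". The reason given for expecting correlated responses is the number per centre: "Since it is planned to recruit up to 10-14 patients per infusion centre for the survey". The example takes the case where "the percentage of correct responses to a question (or the percentage with off-label use) is 75"%. Without correlation, "then for a sample of size 500, the 2-sided 95 CI will be 71.2% to 78.8"%. With correlation 0.3, "the corresponding CI will be 68.3% to 81.7% if there are on average 8 patients per infusion centre".
- **Table 1.** The table note applies the same mean of 8 throughout. Footnote a gives the consequence: "With an average cluster size of 8 patients, correlation coefficients of 0.15 and 0.30 correspond with design effects of 2.05 and 3.1, respectively". Footnote b says the percentage column may stand for any percentage, and names the share of abstractions found to be off-label.
- **Centres.** Section 8.2 plans about 10-15 centres in each country. Section 8.5 caps each centre at 30 patients per component.

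**The concern.** The design effect grows with the number of patients per centre, so a cluster size that is too small makes the interval too narrow. The only component that can reach n = 1,500 is the record abstraction, since the survey aims at 500-700. Those rows therefore show the precision expected for the main off-label analysis in Section 8.6, the proportion of off-label use with its 95% CI. Their cluster size is less than half of the lowest number of records planned per centre.

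Clustering is not a formality for this estimate. Section 8.2 deliberately seeks a mix that includes centres treating mainly off-label patients and centres treating mainly RA patients, so off-label status should be expected to vary between centres.

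**Working it through.** **Inputs.** z = 1.96 (two-sided 95%); p = 0.75 (the protocol's example); intra-class correlations 0.15 and 0.30 (Table 1); m = 8 (Table 1 note); 20-30 records per centre and n = 1,000-1,500 (Section 8.5); 50-75 centres (10-15 in each of 5 countries, Section 8.2). Section 8.1.3 could be read as 10-15 centres in total, but with the cap of 30 that allows at most 15 × 30 = 450 records, so the per-country reading is the one that fits the targets.

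**Formulas.** DE = 1 + (m − 1) × ICC; half-width = 1.96 × √(p(1 − p) × DE / n).

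**Reproducing the protocol.** With m = 8, DE = 1 + 7 × 0.15 = 2.05 and 1 + 7 × 0.30 = 3.1, as in footnote a. For n = 500 and ICC 0.3: 1.96 × √(0.1875 × 3.1 / 500) = 6.68 points, or 68.3-81.7%, as stated. All 36 rows of Table 1 reproduce this way, so the formula is sound and only the input is in question.

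**Is m = 8 possible for records?** 1,500 / 8 = 187.5 centres, against 50-75 planned. In the other direction, 1,500 / 75 = 20 and 1,500 / 50 = 30, exactly the planned 20-30.

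**Records at the planned cluster sizes, p = 75%:**

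| n | per centre | centres | ICC | DE | 95% CI (%) | half-width | Table 1 (m = 8) |
|---|---|---|---|---|---|---|---|
| 1,500 | 20 | 75 | 0.15 | 3.85 | 70.7-79.3 | 4.3 | 71.9-78.1 |
| 1,500 | 30 | 50 | 0.15 | 5.35 | 69.9-80.1 | 5.1 | 71.9-78.1 |
| 1,500 | 20 | 75 | 0.30 | 6.7 | 69.3-80.7 | 5.7 | 71.1-78.9 |
| 1,500 | 30 | 50 | 0.30 | 9.7 | 68.2-81.8 | 6.8 | 71.1-78.9 |
| 1,000 | 20 | 50 | 0.15 | 3.85 | 69.7-80.3 | 5.3 | not tabulated |
| 1,000 | 20 | 50 | 0.30 | 6.7 | 68.1-81.9 | 6.9 | not tabulated |

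At n = 1,500 and ICC 0.3 the half-width rises from 3.9 to 5.7-6.8 points, 47% to 77% wider (√(6.7/3.1) = 1.47; √(9.7/3.1) = 1.77). The effective sample size falls from 1,500/3.1 = 484 to 1,500/6.7 = 224 or 1,500/9.7 = 155. At ICC 0.15 the half-width rises from 3.1 to 4.3-5.1 points.

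**The unclustered records example.** Its half-width is 2.2 points. The planned design gives about 2.0 to 2.3 times that at ICC 0.15 and 2.6 to 3.1 times at ICC 0.3.

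**Records against survey.** At ICC 0.3, 1,000 records at 20 per centre give 68.1-81.9%, no better than the survey's stated 68.3-81.7% from 500 patients. In the same 50 centres, 500 surveys (10 per centre, DE 3.7) give a half-width of 7.3 points, against 6.9 for 1,000 records and 6.8 for 1,500. This assumes the same correlation for both components.

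**Survey, using totals and centre counts that agree (75%, ICC 0.3):**

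- 500 over 75 centres: m = 6.7, DE = 2.7, half-width 6.2.
- 500 over 50 centres: m = 10, DE = 3.7, half-width 7.3.
- 700 over 50 centres: m = 14, DE = 4.9, half-width 7.1.

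The stated 6.7 lies between the two values for 500 surveys.

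**The case against.** A reader might infer that the survey interval, and so every clustered figure in the section, is too narrow because 10-14 per centre exceeds 8. The documents do not support that. The set target of 500 surveys over 50-75 centres averages 6.7-10 per centre, which contains 8, and one sentence words the 10-14 as an upper figure. Holding n at 500 with 12 or 14 per centre would imply about 42 or 36 centres, fewer than the planned minimum of 50. What stands for the survey is an unexplained conflict: 10-14 is also given as the estimate per centre, in Sections 8.2 and 8.5, and 10-14 × 50 centres matches 500-700 surveys.

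Nor is the whole table affected: its 12 rows with zero correlation do not depend on cluster size.

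It can also be said that the value 8 is openly disclosed, that the study is descriptive with no hypothesis test and no precision threshold, that study size rests on feasibility volumes as well as precision, and that Section 8.6 leaves the level of statistical precision to the analysis plan. All of this is true and limits the consequence. It does not rescue the record rows: disclosing an assumption does not make it compatible with the recruitment plan, and these figures are printed in the protocol itself.

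**Conclusion.** Wrong as written for the record component. The eight rows of Table 1 with n = 1,500 and non-zero correlation describe a design with about 188 centres, not the planned 50-75, and they overstate the precision of the off-label estimate. At 75% the true half-width is 5.7-6.8 points rather than 3.9 at ICC 0.3, and 4.3-5.1 rather than 3.1 at ICC 0.15. The worked records example, with no clustering, is more optimistic still, and the claimed precision advantage over the survey largely disappears at ICC 0.3.

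These sizes rest on the protocol's own illustrative correlations and on equal centre sizes. Unequal centre sizes would be expected to widen the intervals further; that was not quantified. The survey's stated interval lies within the range its own targets imply and is not shown to be wrong; only the 10-14 and the 8 need to be reconciled.

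**What to change.** 1. In Table 1, recompute the clustered record rows with 20-30 per centre, at n = 1,000 and n = 1,500, and state the number of centres with each. Pairs that fit the plan are 1,000 at 20 (50 centres), 1,500 at 20 (75 centres) and 1,500 at 30 (50 centres).
2. In footnote a, add the design effects for records: 3.85-5.35 at ICC 0.15 and 6.7-9.7 at ICC 0.30. Limit the note on 8 per centre to the rows it fits.
3. Restate the records example with a design effect, and qualify the sentence that claims more precision than the survey.
4. For the survey, reconcile 10-14 with 8 by giving matching totals and centre counts: 500 over 50-75 centres is 6.7-10 per centre, and 700 over 50 centres is 14 per centre.

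The cost is a recalculation and a text amendment. No extra patients are needed, but the stated records precision becomes less favourable.

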8.6 DATA ANALYSIS

Analysis of MabThera off-label use and evaluation of PAC knowledge and utilisation will be descriptive in nature and will entail the tabular display of summary statistics and the frequency distribution of item responses.

A detailed analysis plan describing methods of analysis and presentation, as well as table shells, will be developed prior to starting analysis of data. In addition to describing the analysis of off-label use, for the questionnaire data, the analysis plan will describe any planned comparisons of participants and non-participants. The analysis plan will also describe the following:

- Analysis of subgroups
- · Methods for handling missing data
- Level of statistical precision

All analyses will be performed using SAS 9.2 (or higher) statistical software (SAS Institute Inc., Cary, North Carolina, USA). Programs, logs, and output will be reviewed for accuracy according to relevant standard operating procedures.

The analysis of off-label use will be descriptive and will present MabThera utilisation by indication (RA, SLE/LN, other). Results will be evaluated by site characteristics, including country and geographic region within country, to ascertain any patterns of prescribing by specific indication. The main analysis will be to estimate (with 95% CIs)

^a With an average cluster size of 8 patients, correlation coefficients of 0.15 and 0.30 correspond with design effects of 2.05 and 3.1, respectively.

^b The percentage in this column does not need to represent only the percentage of correct responses; it can represent any percentage, for example percentage of abstractions that were identified as off-label use or percentage of abstractions that had systemic lupus erythematosus (SLE).

the proportion of off-label use among users of MabThera during the entire study period in the 5 European countries of interest. The proportion of each of the most common off-label use indications will be described among the entire off-label use group. In addition, an estimate of off-label usage will be determined amongst prevalent (i.e., repeat infusions) and incident (i.e., patients attending for their first MabThera infusion) patients to the extent that incident use can be accurately determined. Characteristics of patients meeting the definitions for both strict and broad on-label use will also be evaluated. The dosage of MabThera used by infusion will also be estimated in the on- and off-label groups.

To evaluate the differences between subgroups by indication, with 95% CIs, proportions for categorical variables and means for continuous variables will be estimated within each subgroup. If appropriate, medians will be used instead of means when the variables of interest do not assume a normal distribution.

It is anticipated that the analyses of the PAC knowledge and utilisation will focus on summarising the results of the questionnaire data (e.g., percentage confirming receipt of the PAC, percentage demonstrating correct knowledge of the PAC, percentage correctly identifying the appropriate actions they should take under different scenarios). Tables will include frequencies and percentages for categorical variables and descriptive statistics (e.g., median, means and standard deviations or 95% CIs) for continuous variables (e.g., scales or composite variables created from summation of several items). Results will be grouped by key variables that could be related to patient awareness, such as recency of the first treatment with MabThera and whether the participant reported reading the PAC. Results will also be grouped by the clinical condition for which the patient received MabThera (RA, other autoimmune diseases) in a subset of patients who provided consent for both the questionnaire and medical record abstraction (since information on clinical condition is only provided by the latter). Open-ended responses (if any) will be listed and categorised as appropriate, but will not be analysed quantitatively. In the study report, results will be provided in aggregate form only.

The number of patients who were invited to participate in the survey but declined will be tracked, and the analyses will describe selected key general characteristics of non-respondents (e.g., reason for refusal). Based on the information available on the recruiting logs (i.e., age, sex, and clinical indication), the analysis will compare characteristics of survey respondents with characteristics of patients who refused to participate in the survey. Also, characteristics of the infusion centres participating in the study will be compared with characteristics of the overall set of infusion centres from the final list of infusion centre used, based on the information available for all centres on the list, e.g., geographic location, centre type (clinic, hospital), and physician specialty (internal medicine, rheumatology).

Exploratory analyses will be conducted to examine low awareness of key safety elements based on patients who read the PAC vs. those who did not; patients who were

infused in-office vs. infused at independent infusion centres; and incident MabThera patients (i.e. patients receiving their first course of MabThera) compared with patients who had received 2 or more courses.

Results of both components of the study will be examined to assess any implications for the MabThera communication and education activities, including the PAC, and for physicians and patients on the appropriate use of MabThera. If any findings suggest extensive off-label use or suboptimal patient knowledge of the PAC or patient-reported practice patterns, root cause analyses may be explored, as appropriate (e.g., additional exploratory analyses, follow-up discussions), with infusion centres that participated in the survey. Follow-up contact with infusion centres might examine differences in practices by site type. Results of the study and root cause analyses can be used as input into potential modifications to the MabThera communication and education activities, including the PAC programme.

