6.2 MABTHERA

Rituximab (MabThera®) is a genetically engineered chimeric murine/human monoclonal antibody, which binds specifically to CD20, a B-lymphocyte differentiation antigen on pre-B and mature B-lymphocytes. In June 2006, the United States (US) Food and Drug Administration had approved MabThera for RA (Food and Drug Administration, 2006). In June 2006, the European Medicines Agency (EMA) approved the use of rituximab for the same indication. The RA indication was updated by Variation EMEA/H/C/165/II/65 (EMA, 2010). The current European Union (EU) approved label authorises MabThera in combination with methotrexate for the treatment of adult patients with severe, active RA who have had an inadequate response or intolerance to other disease-modifying anti-rheumatic drugs including one or more tumour necrosis factor (TNF) inhibitor therapies.

In March 2013, the EMA approved a new non-oncology-related indication, allowing the use of MabThera in combination with glucocorticoids for the induction of remission in adult patients with severe, active GPA (Wegener's) and MPA (EMA, 2013a). Rituximab is also approved for several oncology conditions, but these indications are not the focus of this study.

This protocol addresses the 2 EU follow-up measures (FUMs) following approval of Variation EMEA/H/C/165/II/65 for MabThera use in RA.

1. FUM no. 68 (Clinical): Drug Utilisation Study to Assess Off-Label Use

There is concern regarding off-label use of MabThera, in particular that rheumatologists and other physicians may prescribe MabThera for systemic lupus erythematosus (SLE) and lupus nephritis (LN). The EMA Committee for Medicinal Products for Human Use (CHMP) FUM (Clinical) No. 68 from Procedure No. EMEA/H/C/165/II/65 states, 'Given the extensive off-label potential of MabThera, the MAH [Marketing Authorisation Holder] should submit a European drug utilisation study protocol to the CHMP'.

2. FUM No, 71.1 (Pharmacovigilance): Evaluation of Receipt, Use, and Impact of the Patient Alert Card (PAC) on Infections, Including Progressive Multi-focal Leukoencephalopathy (PML)

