8. RESEARCH METHODS

8.1 STUDY DESIGN

8.1.1 Overview of Study Design

This DUS is a multinational, multicentre study involving the retrospective chart review of MabThera users' medical records in non-oncology indications (Figure 1). Nested in the study, a cross-sectional survey of patients receiving MabThera will be performed starting from the date of the first medical record data abstraction (Figure 1).

A geographically dispersed and diverse set of infusion centres in the United Kingdom (UK), Germany, France, Italy, and Spain will be recruited to participate in the study. At each participating centre, de-identified data will be retrospectively abstracted from medical records on treatment indication (RA, SLE/LN, other) and selected patient and disease characteristics for all patients receiving MabThera for a non-oncology condition, during a 10-month data collection period. The survey will also be conducted during the same 10-month period, and will prospectively collect information on patient characteristics, and will include questions about patient knowledge on the risk of infections including PML, patient receipt and review of the PAC, and any actions the patient has taken as a result of receiving the PAC.

Final approved protocol Q2 2015 Q4 2015 Q3 2016 Q1 2017 Start-up Phase Questionnaire Pilot validation Analysis ICF + Data collection (medical abstraction and Country regulatory submissions and parallel survey administration Reporting Site sampling & selection (up to 10 months) (6 months) Site Contracting EDC setup Study period Inception cohort of all patients treated with Mabthera in NO prior the index date Index date (country & site Last patient data Final report to specific): PRAC (March 27 abstracted Start of the first Medical record 2017) & Data lock data abstraction

Figure 1: DUS and PAC Survey Overview

ICF: Informed Consent Form; NO: non-oncology conditions; PRAC: Pharmacovigilance Risk Assessment Committee; Q: quarter.

Drug Utilisation Study

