8.3 VARIABLES

Medical Record Data

The site will abstract information from the medical record for each of the DUS consenting patients and will enter the abstracted information in an electronic case report form (eCRF):

- Study ID (identification), age, sex
- Condition for which MabThera has been prescribed (via checklist):

- RA
- Ankylosing spondylitis
- Psoriatic arthritis
- Undifferentiated spondyloarthritis
- Juvenile idiopathic arthritis
- SLE
- Systemic vasculitis
- Inflammatory myopathies
- Behçet disease
- Sjögren syndrome
- Nephrotic syndrome
- Reason for MabThera prescription:
 - Failure of previous treatment
 - Adverse events (AEs) under previous treatment
 - Compassionate use
- Date of first diagnosis of the condition
- For patients with RA, severity of RA as measured with the DAS28 (28-joint Disease Activity Score). To calculate the DAS28, the following items will have to be abstracted from the medical record:
 - C-reactive protein level
 - Erythrocyte sedimentation rate
 - Number of tender joints
 - Number of swollen joints
 - Global assessment of patient's general health on the visual analogue scale (VAS) (0–100)
 - Presence of extra-articular involvement
- MabThera dosage for the most recent infusion and number of MabThera infusions in the past 2 years
- Other current and previous anti-inflammatory medication including biological agents other than MabThera
 - Methotrexate (key variable for on- or off-label classification of MabThera use)

- Glomerulonephritis
- Multiple sclerosis/neuromyelitis optica
- Pemphigus vulgaris
- Polydermatomyositis
- Mixed connective tissue disease
- Wegener's GPA/ MPA
- Eosinophilic GPA
- Other (specify)

- Immunosuppressives: prednisolone, glucocorticoid bolus therapy, methylprednisolone, methotrexate, cyclophosphamide, azathioprine, mycophenolate mofetil, intravenous immunoglobulin, plasmapheresis, other immunosuppressives (specify)
- Non-steroidal anti-inflammatory drugs (NSAIDs), including cyclooxigenase (COX)-2 inhibitors
- Biological agents:
 - TNF-alpha inhibitors (key variable for on- or off-label classification of MabThera use): etanercept, infliximab, adalimumab, golimumab, certolizumab pegol, ocrelizumab
 - Interleukin inhibitors: tocilizumab, anakinra
 - Abatacept
 - Janus kinase (JAK) inhibitor: tofacitinib
 - Other biological agents (specify)

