A "data not available" response will be available where appropriate for those record abstraction items for which data may be missing from patient records. This type of response will help reduce missing data and will document the overall gaps in record keeping.

A brief pilot test of the translated version of the abstraction form will be conducted in each country, and the abstraction form in one or more countries may be adjusted based on the results of this pilot.

A draft version of the medical record abstraction form is included with this document (Appendix 1).

Off-Label Use Definition

The definition of off-label use of MabThera will be based on the use for a non-oncology disease or medical condition other than RA and GPA/MPA covered by MabThera SPC.

In absence of labelled indications, potential off-label use could include, but is not limited to, the following conditions:

- Ankylosing spondylitis
- Psoriatic arthritis
- Undifferentiated spondyloarthritis
- Juvenile idiopathic arthritis
- SLE
- Systemic vasculitis

- Eosinophilic GPA
- Inflammatory myopathies
- Behçet disease
- Sjögren syndrome
- Nephrotic syndrome
- Glomerulonephritis
- Multiple sclerosis/neuromyelitis optica
- · Pemphigus vulgaris
- Polydermatomyositis
- · Mixed connective tissue disease

Patient Survey data

The patient questionnaire has been developed following standard survey methodological principles and will be cognitively tested with patients in each of the target countries. Modifications will be made to the questionnaire based on the results of testing, and some variations to the questionnaire are anticipated based on country-specific requirements.

The questionnaire will include an introductory section with questions to confirm eligibility. The majority of the questionnaire items will be closed ended, ensuring that the resulting data are easy to analyse and interpret. Closed-ended questions are generally more efficient than open-ended questions (or open-ended text fields) and more conducive to summarisation and statistical analyses.

The questionnaire will collect the following information (please refer to Appendix 1 for the draft questionnaire):

- Demographics (e.g., age, sex, ethnicity)
- Patient previous history of PML or other serious infectious diseases
- Whether the patient has received a previous treatment with MabThera, if so, number of prior infusions during the last 12 months
- Patient understanding or awareness of the following:

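### The indication categories blur on-label and off-label use: GPA/MPA falls in 'other', lupus nephritis has no entry, and the 'systemic vasculitis' box overlaps GPA/MPA

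*Protocol*

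**What the plan says.** **Regulatory question.** Section 6.2 gives the concern behind the drug utilisation part: physicians "may prescribe MabThera for systemic lupus erythematosus (SLE) and lupus nephritis (LN").

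**Definition.** Section 8.3: "The definition of off-label use of MabThera will be based on the use for a non-oncology disease or medical condition other than RA and GPA/MPA". RA and GPA/MPA are therefore the on-label diseases.

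**Data capture.** Section 8.3 collects the "Condition for which MabThera has been prescribed (via checklist"). The list includes SLE, nephrotic syndrome, glomerulonephritis, systemic vasculitis, a GPA/MPA box, an eosinophilic GPA box and a free-text 'other'. It has no entry for lupus nephritis. Item 7 of the draft abstraction form (Appendix 1) asks for one primary condition. The list of potential off-label conditions in Section 8.3 contains "Systemic vasculitis" with no qualifier.

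**Reporting.** The same three groups appear in Section 8.1.1 ("medical records on treatment indication (RA, SLE/LN, other")), in Section 8.5 ("estimates of MabThera use by whether the disease indication (RA, SLE/LN, other) represents on-label or off-label use") and in Section 8.6 ("The analysis of off-label use will be descriptive and will present MabThera utilisation by indication (RA, SLE/LN, other")). Section 8.6 separately plans the overall off-label proportion with a 95% CI, as the main analysis, and the common indications within the off-label group.

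**The concern.** Specific aim 1 is to quantify and characterise off-label use, so the variable that classifies each record has to be unambiguous. Three features work against that.

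1. The three reporting groups leave out one of the two on-label diseases. 'Other' then mixes on-label and off-label use, although Section 8.5 presents the grouping as showing label status.
2. The protocol promises an SLE/LN group, but the form cannot identify lupus nephritis directly. Such a patient could reasonably be filed under SLE, glomerulonephritis, nephrotic syndrome or free-text 'other'.
3. Section 6.1 describes GPA and MPA as small-vessel vasculitides, so the systemic vasculitis and GPA/MPA boxes are not mutually exclusive. A chart that says only ANCA-associated or systemic vasculitis could be ticked in the box listed as potential off-label.

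The first concerns presentation. The second touches the use that the regulator named. The third can reach the main estimate.

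**Working it through.** **1. The plan's own precision figure.** Section 8.5 gives 72.8% to 77.2% for 75% on-label at n = 1,500. The Wald half-width is 1.96 × √(0.75 × 0.25 / 1,500) = 2.2 points, so 75% ± 2.2 reproduces the interval. The half-width is the same for 25% off-label. Table 1 uses design effects of 2.05 and 3.1 (cluster size 8, intra-class correlation 0.15 and 0.3). The half-widths become 2.19 × √2.05 = 3.1 and 2.19 × √3.1 = 3.9 points, matching the table's 71.9-78.1 and 71.1-78.9.

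**2. Systemic vasculitis overlap.** The documents give neither the GPA/MPA share of records (g) nor the fraction of those ticked as systemic vasculitis (m). Both are assumed here. True off-label use is set at 25%, the complement of the protocol's example. Apparent off-label use = 25% + g × m. The shift g × m in points is:

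| g | m = 10% | m = 20% | m = 30% | m = 50% |
|---|---|---|---|---|
| 5% | 0.5 | 1.0 | 1.5 | 2.5 |
| 10% | 1.0 | 2.0 | 3.0 | 5.0 |
| 15% | 1.5 | 3.0 | 4.5 | 7.5 |
| 20% | 2.0 | 4.0 | 6.0 | 10.0 |

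Apparent off-label use runs from 25.5% to 35.0%. The shift exceeds 2.2 points in 9 of the 16 cells, and exceeds 3.9 points in 6. For GPA/MPA patients the error goes one way only, and it does not shrink with more records.

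**3. Content of 'other'.** Let s be the SLE/LN share, assumed 5-10%. 'Other' holds g plus the remaining off-label use, 25% − s, so the on-label fraction of 'other' is g / (g + 25% − s).
- Lowest: g = 5%, s = 5% gives 5/25 = 20%.
- Highest: g = 20%, s = 10% gives 20/35 = 57%.

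Someone who took everything outside RA as off-label would read 25% + g, that is 30% to 45%.

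**4. Lupus nephritis.** SLE, glomerulonephritis and nephrotic syndrome are all off-label under Section 8.3, so filing among them changes total off-label use by zero. The loss from the SLE/LN group is s × (fraction with nephritis) × (fraction ticked in a renal box). With one third and one half assumed for the two fractions:
- s = 5% loses 5 × 1/3 × 1/2 = 0.8 points.
- s = 10% loses 1.7 points, so 10% is reported as 8.3%.
- If every such patient is filed under SLE, the loss is zero.

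**The case against.** The strongest reply is that the main result does not use the three groups. It follows the Section 8.3 definition, and GPA/MPA has its own box. Section 8.6 also breaks down the off-label group by indication and compares dosage in on- and off-label users. That stands. A reader might infer that the study cannot separate on-label from off-label use, and the documents do not support this. The failure is confined to the by-indication grouping, which a later analysis plan could regroup.

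Second, misfiling is not shown to occur. There are dedicated boxes for GPA/MPA and eosinophilic GPA, so systemic vasculitis can be read as the residual. The list is headed as potential off-label use, the form is a draft to be piloted in each country, and entries are verified against records (Section 8.7.2). This also stands: undercounting of SLE/LN and inflation of off-label use are risks, not facts. The reply does not remove them. A tick in the vasculitis box agrees with a chart that says only vasculitis, so verification need not flag it. Nor can an analysis plan recover a status that a single-choice form never captured. Free-text 'other' recovers only the cases entered there.

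Third, a reader might extend the point to the survey, where results are "grouped by the clinical condition for which the patient received MabThera (RA, other autoimmune diseases"). Aim 2 concerns receipt, reading and knowledge of the alert card and patient actions, not label status, and that split is not offered as an on-/off-label comparison. Section 8.6 openly states its restriction to patients consenting to both components. Regrouping the survey or adding an indication question would be a preference.

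Finally, it is tempting to say that the three groups are left over from before the GPA/MPA approval. The earlier protocol text is not shown, so this remains conjecture.

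**Conclusion.** The point holds in three parts of unequal weight.

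- **Grouping:** a definite inconsistency. The groups in Sections 8.1.1, 8.5 and 8.6 cannot show label status, because on-label GPA/MPA sits in 'other'. The overall off-label proportion is untouched.
- **Lupus nephritis:** a possible understatement of the SLE/LN share, with no effect on total off-label use. This relies on the list in Section 8.3, because some condition labels on the draft form are cut off in the text at hand.
- **Systemic vasculitis:** a possible upward bias in the main estimate. It ranges from trivial (0.5 points) to well beyond the planned half-width (10 points). The upper end needs GPA/MPA at 20% of records, with half mis-ticked despite a dedicated box.

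All shares in the calculation are assumptions. The point ranks below a must-fix, but the data-capture part should be settled before abstraction starts.

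**What to change.** - In Sections 8.1.1, 8.5 and 8.6, report four groups: RA; GPA/MPA; SLE/LN; other off-label.
- In Section 8.3 and item 7 of the draft form, make the SLE entry explicitly include lupus nephritis, or split it into SLE with and without nephritis.
- Relabel the glomerulonephritis and nephrotic syndrome boxes as not due to lupus.
- Relabel the vasculitis box as systemic vasculitis other than GPA, MPA or eosinophilic GPA, and make the same change in the list of potential off-label conditions.

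The cost is a few labels, their translations and the table shells, on a form that is still a draft awaiting its pilot. No change to the survey or the questionnaire is needed.
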